Obesity (a body mass index ≥ 30 and waist to hip ratio of at least 0.9 in males and at least 0.85 in females) has been correlated with higher mortality risk and is associated with a proinflammatory state (e.g. elevated levels of TNF-alpha and interleukin-6). Obesity has also been associated with a lower immune response to various types of vaccination (e.g. influenza, hepatitis B, tetanus). As the prevalence of obesity increases, so does the need for a deeper mechanistic understanding of how obesity attenuates vaccination response. It is important to assess the effect of obesity on the immune response to vaccines. The pneumococcal polysaccharide vaccine (Pneumovax 23) is a safe method for stimulating an immune response and its effect on obesity has not been elucidated. As a growing population of obese individuals inevitably age and become susceptible to pneumococcal infections, it is important to consider how obesity may impact the efficacy of Pneumovax 23. We hypothesize that a chronically stressed immune system in obese individuals will be unable to respond as well to vaccination compared to individuals with a BMI between 22 and 25. We will utilize a prospective cohort design. We will also conduct various surveys to examine psychosocial factors that may influence the interaction between obesity and immune response to vaccination. We will also perform genotyping of STING to assess how it may influence the relationship between obesity and immune response to vaccination.

2. HYPOTHESIS AND SPECIFIC AIMS:

The primary objective of this study is to demonstrate the effect of obesity on the immune system's ability to mount a protective immune response against the Pneumococcal Polysaccharide Vaccine (Pneumovax 23).

Primary Hypothesis (stated as null): Levels of antibodies to serotypes in Pneumovax 23 in pre- and post- vaccination in individuals with a BMI between 22 and 25 and obese individuals are identical.

Secondary Hypothesis (stated as null): Levels of pro- and anti-inflammatory cytokine levels pre- and post-vaccination in individuals with a BMI between 22 and 25 and obese individuals are identical.

Tertiary Hypothesis (stated as null): The perceived level of stress, loneliness, social support, and dispositional optimism will be the same between the group of individuals with a BMI between 22 and 25 and the group of obese individuals, or between groups with different immune responses to the vaccine.

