Quaternary Hypothesis (stated as null): Those who carry *STING* variants and those who are wildtype *STING* carriers will not have differing immune responses to Pneumovax 23.

Specific Aim 1: Quantify changes in the adaptive immune response to Pneumovax 23 by measuring specific antibodies to Pneumovax 23 antigens pre- and post-vaccination in the group of individuals with a BMI between 22 and 25 and the group of obese individuals.

Specific Aim 2: Quantify changes in the inflammatory immune response to Pneumovax 23 by measuring C-reactive protein (CRP) and cytokines pre- and post-vaccination in the group of individuals with a BMI between 22 and 25 and the group of obese individuals.

Specific Aim 3: Determine if perceived stress, loneliness, social support, and dispositional optimism are associated with adaptive immune response to Pneumovax 23.

Specific Aim 4: Determine how *STING* genotypes may affect the adaptive immune response to Pneumovax 23.

3. BACKGROUND AND SIGNIFICANCE:

Pneumococcal infections are a leading cause of adult and childhood hospitalization and mortality with an estimated 1.6 million deaths occurring annually.^{1,2} Prophylactic measures against pneumococcal infections exist in the form of a vaccine called Pneumovax 23. While Pneumovax 23 is approved for use in all adults 50 years or older and individuals as young as 2 years who are at increased risk for infection, the vaccine is recommended for all adults 50 years and older or adults age 19 to 64 with conditions or treatments that affect the immune system.³ These recommendations were developed, in part, from a 14-year cohort study comparing the proportion of pneumococcal infections caused by varying pneumococcal serotypes included in vaccinated and unvaccinated individuals.⁴ Pneumovax 23 had an overall efficacy rate of 57% in preventing pneumococcal infection. In addition to recommending the vaccine to the elderly, the vaccine is also recommended for individuals who have been identified as being at higher risk for contracting pneumococcal pneumonia, such as those infected by human immunodeficiency virus.⁵ Increased weight gain and a high body mass index have been associated with an increased risk for contracting pneumococcal pneumonia, suggesting it is desirable to provide effective vaccination of this susceptible population.⁶

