Studies have shown that obesity is implicated in decreased immunological responses to hepatitis B, tetanus, and influenza vaccines.^{8,9,10} For example, obesity is associated with a lower vaccine-specific IgG titer (<10mIU/mL) following hepatitis B vaccination.¹¹ Furthermore, obesity alters the metabolic and endocrine status of individuals that leads to immune dysfunction.¹² Current evidence suggests that a number of proinflammatory markers and tests are elevated in obesity such as TNF, IL-6, CRP, and erythrocyte sedimentation rate.^{13, 14, 15} This pro-inflammatory state may attenuate the initial humoral immune response that vaccinations provide.⁹ Additionally, obesity has been associated with a pro-inflammatory state (elevated levels of TNF-alpha and interleukin 6), impaired natural killer cell activity, decreased CD8+ T cell populations, and decreased response to antigen stimulation, which may affect responses to vaccination (Figure 1).^{16,17,18} Immunizations in obese patients may also be ineffective due to an inadequate needle length in depositing the vaccine intramuscularly through subcutaneous fat tissue.¹⁸

No current studies have examined the effects obesity may have on the response to pneumococcal vaccine in humans. We hope to initiate an observational prospective cohort study to investigate the effect of obesity on immune responses in individuals vaccinated with Pneumovax 23.

[figure not shown]

Figure 1. Mechanism of Obesity on Immune Response to Vaccination. Modified from Hur *et al.*, 2013.

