2. Study Design: Participants will be asked to fast after midnight prior to the first blood draw. A baseline blood draw (39 mL) will be performed for each participant. Pneumovax 23 will then be administered into the deltoid muscle by the CRC nurses; needle length will be adjusted according to distance from skin surface to muscle bundle. The Pneumovax 23 vaccine will be provided by the University of Florida Investigational Drug Services. They receive their commercial products from McKesson Pharmaceuticals. Effort will be taken to ensure that all participants receive the same lot number of Pneumovax 23.

Blood will be drawn 4-6 weeks following vaccination, as primary antibody production peaks during this time frame.⁴⁰ At that time, a total of 33 mL of blood will be drawn for analyses of antibody and cytokine levels. Table I illustrates what assays will be performed on the blood drawn at each time point and Table II illustrates the schedule of each blood draw. Figure 2 outlines a progression of events that will occur during both the screening and the first visit.

[figure not shown]

Figure 2. Progression of events during Visit 1:
Consenting, screening confirmation, blood draw,
vaccination, survey administration, and payment distribution

B. Measurements to be Collected

1. Basic Demographics (e.g. gender, age, race, ethnicity, education, etc.) will be collected.
2. Height, weight and hip-waist circumference will be collected.
3. Baseline Characteristic Assessments: Pregnancy will be evaluated by urine test, and hemoglobin A1C level will be determined with a portable finger-prick monitor.
4. Whole Blood Lab Assays: The following whole blood lab assays will be sent to and performed by Shands Laboratory: total IgG titers, complete metabolic panel, erythrocyte sedimentation rate, and complete blood count (CBC).
5. Anti-pneumococcal Antibodies: IgG antibody titers specific for each serotype in Pneumovax 23 (i.e. 1, 2, 3, 4, 5, 6B, 7F, 8, 9N, 9V, 10A, 11A, 12F, 14, 15B, 17F, 18C, 19F, 19A, 20, 22F, 23F, and 33F) will be analyzed using a panel ordered through the Mayo Clinic.
6. Serum Analyte Measurements: ELISA will be used to measure various acute phase reactants (e.g. TNF, C reactive protein, interferons, interleukins, etc.) and Ig subclasses. If significant

differences are not observed between arms then a cytometric bead assay may be employed. ELISAs will be performed in [name] lab.

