5. STATISTICAL DESIGN AND CONSIDERATIONS

A. Design

The study will include a control and experimental group. Briefly, the control group consists of healthy, normal-weight individuals and the experimental group consists of obese individuals. After passing an

initial screening, eligible participants will be asked to come in for the first of two visits. During the first visit, informed consent will be reviewed, and the informed consent form will be signed. Subsequently, vital signs, patient history, blood, and other baseline measures will be taken. If the urine pregnancy test and A1C test (< 6.5%) confirm the initial screen results, and if the physical exam and history findings are satisfactory, participants will receive a single dose of Pneumovax 23. The participants will then return for one additional blood draw 4-6 weeks after the first visit. The participants will be physically present for a total of 2 visits and will experience 2 total blood draws. If at any time participants become pregnant, diabetic, or are found to have any conditions listed in the exclusion criteria as revealed by CBC, CMP, or physical exam, then subjects will be indicated as screening failures and will not be included in data analysis due to failure to meet inclusion criteria.

B. Hypotheses

Primary Hypothesis (stated as null): Levels of antibodies to serotypes in Pneumovax 23, in pre- and post- vaccination in healthy BMI individuals and obese individuals are identical.

Secondary Hypothesis (stated as null): Levels of pro- and anti-inflammatory cytokine levels pre- and post- vaccination in healthy weight obese and groups are identical.

Tertiary Hypothesis (stated as null): The perceived level of stress, loneliness and social support will be the same between the healthy weight and obese groups or between groups with different immune responses to the vaccine.

Quaternary Hypothesis (stated as null): Those who carry STING variants and those who are wildtype STING carriers will not have differing immune responses to Pneumovax 23.

C. Statistical Methods

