To test the primary hypothesis, we will use the Mayo criteria for positivity of 23 titers, with the primary outcome being the number of positives. We shall employ a two-sided ANCOVA, adjusting for age and gender to compare the obese cases to the non-obese controls. Secondarily, we will compare the 23 individual quantitative titers by similar ANCOVA analyses. Other endpoints will be analyzed in a similar manner as tertiary outcomes.

D. Randomization

No randomization will be done in this study.

E. Sample Size

We expect that 23 evaluable obese participants and 23 evaluable normal weight participants will complete the study. To accommodate for 20% attrition rate we will recruit 28 obese participants and 28 normal participants for a total of 56 eligible subjects. Additionally, to accommodate for individuals unable to participate due to exclusion criteria or individuals eliminated post-enrollment due to screening failure (e.g., CBC/CMP abnormalities), we plan to screen an additional 30 subjects. This accounts for a total of 86 individuals screened. Using information from the 2013-2014 MD-PhD study, we compared those with BMI <25 vs. those with BMI > 25. The distribution of Positive titers amongst the 14 was as follows:

BMI	5	6	7	8	9	10	11	12	Total
<25	1	2	0	2	2	1	4	2	14
>25	0	2	3	0	1	1	0	0	7

This should be viewed as conservative, as we will have greater separation of BMI values than the prior study. The actual gain in power cannot be quantified.

F. Technical Support

Under a CTSI voucher, [name] assisted with the statistics and data analysis. [name] co-authored the statistical section with the students. We will use CTRB facilities for blood draw, temporary tissue storage, and basic lab protocols. The laboratory of [name], MD, will be used to perform experimental procedures including the ELISA assays for IgG quantification.

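### The secondary null compares cytokine levels before and after vaccination, so an existing obesity-related gap could reject it with no difference in response; Aim 2 needs a null on change.

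*Protocol*

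**What the plan says.** - **Hypothesis.** Protocol section 2 gives the secondary null as "Levels of pro- and anti-inflammatory cytokine levels pre- and post-vaccination in individuals with a BMI between 22 and 25 and obese individuals are identical". Section 5.B repeats it with the same structure: "Levels of pro- and anti-inflammatory cytokine levels pre- and post- vaccination in healthy weight obese and groups are identical".
- **Aim.** Specific Aim 2, which this null serves, is to "Quantify changes in the inflammatory immune response to Pneumovax 23 by measuring C-reactive protein (CRP) and cytokines pre- and post-vaccination". Its subject is change.
- **Background.** Section 3 states that "a number of proinflammatory markers and tests are elevated in obesity such as TNF, IL-6, CRP, and erythrocyte sedimentation rate". The opening summary also names TNF-alpha and interleukin-6 as raised. No size is given for any of these differences.
- **Analysis.** Section 5.C describes a two-sided ANCOVA of the number of positive titers on group, adjusted for age and gender, then similar ANCOVAs of the individual titers. Everything else is covered by one sentence: "Other endpoints will be analyzed in a similar manner as tertiary outcomes". It names no visit, change score, baseline covariate or analyte.
- **SAP.** The Outcomes section lists only serotype-specific IgG. The Statistics section applies fold change to titers. There is no cytokine outcome or cytokine analysis. P values in secondary analyses are to be left uncorrected.
- **Analytes.** Section 4.B item 6 says ELISA will "measure various acute phase reactants (e.g. TNF, C reactive protein, interferons, interleukins, etc.) and Ig subclasses", and that a cytometric bead assay may follow if no significant difference between arms is seen. Table 1 adds IL-6, IL-12 and IL-4, again as an open list.

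**The concern.** The hypothesis and the aim ask different questions. Equality of levels at both visits is false as soon as the groups differ before anyone is vaccinated, and the background expects exactly that for TNF and IL-6 (and for CRP, which enters through Aim 2). Equality of change is what would show whether obesity alters the inflammatory response to Pneumovax 23.

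Nothing in the stated analysis closes the gap. The model to be copied has no baseline term, and fold change, which would remove a standing proportional difference, is specified for antibodies only. An analyst following the text could compare Visit 1 levels, Visit 2 levels or changes, and each answers a different question. A significant level comparison could be reported as an altered response to the vaccine when it only restates the background section. The open analyte list, with no correction planned, adds further ways to reach p < 0.05.

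**Working it through.** **1. The plan's own figure.** The 23 per group comes from the titer table (protocol 5.E; SAP, Sample size calculation).
- BMI < 25: 129/14 = 9.214. BMI > 25: 52/7 = 7.429. Difference 1.786.
- SDs 2.326 and 1.512. Pooled SD = √[(13 × 2.326² + 6 × 1.512²)/19] = 2.104, so d = 1.786/2.104 = 0.849.
- Two-sided t test, alpha 0.05, 80% power: n = 22.8, so 23 per group. Power at 23 is 80.4%.

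The figure reproduces, but it concerns the number of positive titers. No figure is given for cytokines.

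**2. Inputs for the check.** From the documents: 23 evaluable per group and two-sided alpha 0.05. Assumed, because the documents give no size: a standing gap of δ SD, the same at both visits (so there is no difference in change), and a within-person correlation ρ between visits.

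**3. Comparing levels at one visit.** The test statistic is noncentral t with 44 degrees of freedom and noncentrality δ√(23/2) = 3.391δ; the critical value is 2.015. Removing 2 degrees of freedom for age and sex leaves these percentages unchanged.

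| Assumed gap δ (SD) | Noncentrality | P(reject), one visit | P(reject), Visit 1 or Visit 2 (ρ 0.7 to 0.5) | P(reject), change score |
|---|---|---|---|---|
| 0.2 | 0.68 | 10% | 16–17% | 5% |
| 0.5 | 1.70 | 38% | 50–54% | 5% |
| 0.8 | 2.71 | 76% | 86–89% | 5% |
| 1.0 | 3.39 | 91% | 96–97% | 5% |

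The either-visit column is simulated (20,000 runs). The change-score column follows directly: the gap δ is in both visits and cancels in the difference, so the test keeps its nominal 5% (simulated 4.8% to 5.2%).

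**4. Adding baseline as a covariate instead.** In groups that were not randomised, this removes only ρδ of the gap and leaves (1 − ρ)δ. At δ = 0.5 that is 0.10 for ρ = 0.8 and 0.20 for ρ = 0.6, with simulated rejection of about 8% and 12–13%. At δ = 0.8 the rates are about 13% and 22–24%.

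**5. Several analytes.** The cytokines named or implied are TNF, an interferon, IL-4, IL-6 and IL-12. With no true difference and independent tests at 0.05, the chance of at least one p < 0.05 is:
- five cytokines: 1 − 0.95⁵ = 23%
- six analytes, with CRP: 1 − 0.95⁶ = 26%
- six analytes with a common correlation of 0.5: 21% (simulated)

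These are for one time point and a closed list. The list is open, so the true number of tests is unknown.

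**The case against.** The strongest reply is that section 5.C does not fix the cytokine outcome as the raw Visit 2 level. Aim 2 speaks of change, and the SAP uses fold change for titers, so the investigators may well have meant change throughout. A reader might infer that the plan commits to a raw Visit 2 comparison and that a baseline gap will be counted as a vaccine effect. The documents do not support that. The percentages in the table are conditional on levels being compared and on gaps that are assumed. What stands is that the null is worded on levels in two places and that no text commits the cytokine analysis to change.

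Three other stronger readings also fail:
- **A larger error rate.** Counting the four IgG subclasses and IgM with the six analytes gives 11 tests and 1 − 0.95¹¹ = 43%. Immunoglobulins cannot reject a null about cytokines. Nor do the documents say that one significant analyte would reject the whole hypothesis.
- **An explicit exemption from correction.** The SAP sentence concerns secondary analyses and follows the STING and psychosocial analyses, while section 5.C calls the remaining endpoints tertiary. No correction for cytokines is planned, but an express exemption is an inference.
- **An effect on the primary result.** Sample size and primary analysis are untouched, and section 4.E calls the study a pilot.

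It is also fair to say that baseline inflammation is a legitimate target, since section 3 proposes that it may weaken the antibody response. Reporting Visit 1 and Visit 2 separately would make a standing gap visible. That argues for describing the Visit 1 difference, not for combining it with response in one null. Section 4.F limits conclusions to association, but this does not separate higher IL-6 in obesity from a different response to the vaccine.

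**Conclusion.** The point holds, conditionally. As worded, the secondary null can be rejected with no difference in the inflammatory response, and neither document specifies an analysis that prevents it. If levels are compared at one visit with 23 per group, rejection runs from 10% at a 0.2 SD gap to 91% at 1.0 SD, against 5% for change. The size of the gap is an assumption; its direction, for TNF, IL-6 and CRP, is the protocol's own. The multiplicity element is smaller: at most 23% for five named or implied cytokines and 26% with CRP, at one time point, under independence.

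This affects how a non-primary result is interpreted. It should be corrected, but it does not threaten the trial's main comparison.

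**What to change.** 1. Restate the secondary null in protocol sections 2 and 5.B, and add it to the SAP: the change from Visit 1 to Visit 2 in CRP and in a pre-listed set of pro- and anti-inflammatory cytokines is the same in both BMI groups.
2. Analyse log(Visit 2/Visit 1) by group with age and sex. This matches the SAP's fold change for titers.
3. Name the analytes before analysis, covering both the pro- and anti-inflammatory sides of the hypothesis, and say how multiplicity across the list is handled.
4. Report the Visit 1 group difference separately, as a description of baseline inflammation.
5. Report analytes not on the list, and any bead-assay repeat prompted by a non-significant ELISA result, as exploratory.

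**Cost.** Protocol and SAP wording only; Table 1 already schedules cytokine samples at both visits. There are two downsides. Fewer results can be called significant. And log change measures relative, not absolute, response: an equal rise of 1 unit from baselines of 2 and 4 gives ln(3/2) = 0.41 and ln(5/4) = 0.22. Baseline-adjusted ANCOVA answers a different question; if it is preferred, the SAP should say so and acknowledge the residual effect of the baseline gap.

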In addition to the factors that alter the immune response in obesity, various psychosocial factors such as stress, loneliness, social support and dispositional optimism have been documented to influence the immune system. Studies have shown stress-related dysregulation of the immune system is large enough to impact health.^{19,20} Specifically, stress has been shown to be associated with decreased immune response to vaccination such as less seroconversion, lower IgG antibody response, and down-regulation of the immune response.^{21,22,23} Loneliness, too, has been shown to be associated with poorer antibody response to the influenza vaccine and impaired cellular immunity.^{24,25} Greater social support appears to generate a stronger immune response to a vaccine²¹ and is related to lower levels of interleukin-6.^{26,27,28} Lastly, dispositional optimism has been associated with higher numbers of cytotoxic and helper T cells, higher lymphocyte count^{29,30} and lower interleukin-6 response. When more optimistic individuals were given a typhoid vaccine, they exhibited greater antibody response.³¹ No current studies have yet examined the interplay of obesity, stress, loneliness, social support, and dispositional optimism in response to the same vaccination.

Another consideration that may affect immune responses to vaccination include a person's STING variants. Animal studies have shown that Pneumovax23® efficacy is controlled by a gene called STING (stimulator of interferon genes)⁴¹. Human STING gene shows significant heterogeneity and population stratification⁴². Using animal models of human STING variants and human B cells from various human STING gene carriers, [name] group discovered that human STING variants influence the efficacy of Pneumovax23®. These human STING genotypes account for ~10% of Caucasians, ~14% of Africans, ~18% of South Americans and ~30% of East Asians. These variants may therefore play a role in how participants' immune system respond to the vaccine.

4. RESEARCH PLAN & METHODS:

A. Experimental Design

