The primary outcome measure for the power calculation was the number of positive pneumococcal titers using data from Wildes et al. (2019). This study included a range of BMIs under 30. By comparing the number of positive titers between those with a BMI < 25 and > 25, we expect that 23 evaluable obese participants and 23 evaluable normal weight participants will provide enough power for the study (see the distribution of positive titers below in Table 1) at a significance level of $\alpha = 0.05$ for a 2-sided t test at 80% power. We consider this estimation to be conservative, as we expect that having a greater separation of BMI values than Wildes et al. will provide greater power. The actual gain in power cannot be quantified.

Table 1. The distribution of positive titers amongst the 14 in Wildes et al. study was as follows:

BMI	5	6	7	8	9	10	11	12	Total
<25	1	2	0	2	2	1	4	2	14

>25	0	2	3	0	1	1	0	0	7
-----	---	---	---	---	---	---	---	---	---

Aims and objectives

The aim of this project is to investigate the effect of obesity on the immune system's ability to mount a protective immune response against the pneumococcal polysaccharide vaccine (Pneumovax 23).

Outcomes

Primary outcome: Vaccine response as measured by serotype-specific IgG antibody responses against the 23 pneumococcal serotypes (i.e., 1, 2, 3, 4, 5, 6B, 7F, 8, 9N, 9V, 10A, 11A, 12F, 14, 15B, 17F, 18C, 19A, 19F, 20, 22F, 23F, 33F)

Statistics:

When comparing between populations (ie. baseline characteristics table), normality was first assessed by the Shapiro-Wilk test, then followed by either an unpaired 2-sided t test or a Wilcoxon's signed-rank test for parametric data or nonparametric data, respectively. Chi-square tests determined differences in categorical data (i.e. sex, ethnicity). For our primary analysis, we will use an ANCOVA to test for differences in fold change titer levels across groups (nonobese and obese), controlling for sex and age. All hypothesis tests were 2-sided where a P value < 0.05 was considered significant.

To assess the role of the STING genotype, a secondary analysis will be done using 2-way ANOVA of the fold change in titer levels between the wildtype, R232/R232, and HAQ carrier genotypes. Likewise, to assess the role of psychosocial variables, we will also be using an ANOVA or regression, as appropriate. For secondary analyses, we will not perform any multiple testing corrections for P values.

References

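### The STING genotype analysis lists no race/ethnicity term, so part of any ancestry difference in titre response can appear as a STING effect

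*Protocol*

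**What the plan says.** Protocol section 3 (Background and Significance) states "Human STING gene shows significant heterogeneity and population stratification" and then gives the frequencies: "These human STING genotypes account for ~10% of Caucasians, ~14% of Africans, ~18% of South Americans and ~30% of East Asians". Section 4.B (Measurements to be Collected) says "Basic Demographics (e.g. gender, age, race, ethnicity, education, etc.) will be collected".

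The SAP's Statistics section plans a "2-way ANOVA of the fold change in titer levels between the wildtype, R232/R232, and HAQ carrier genotypes". It names no covariates for this analysis and does not say what the second factor is. Its primary model is an ANCOVA "controlling for sex and age". Protocol section 5.C likewise says "We shall employ a two-sided ANCOVA, adjusting for age and gender to compare the obese cases to the non-obese controls" and treats other endpoints in a similar way. The SAP's only stated use of ethnicity is a chi-square comparison between populations, as for the baseline table. The eligibility criteria do not restrict by ancestry, and there is no randomization.

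**The concern.** Aim 4 asks how STING genotype may affect the antibody response. Genotype is observed, not assigned, and by the protocol's own account it is unevenly spread across ancestry groups. If titre response also differs by ancestry for reasons other than STING, variant carriers and wildtype participants will differ in response even when STING does nothing. The variable needed to reduce this is already collected, but the plan does not use it. Secondary P values are uncorrected, so nothing else in the plan guards against a spurious genotype finding.

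**Working it through.** **Inputs from the documents.** Variant frequency is 10% (Caucasian), 14% (African), 18% (South American) and 30% (East Asian), and 30/10 = 3.0. Evaluable N is 23 + 23 = 46.

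The 23 per group reproduces from the titre table. The means are 9.21 and 7.43, the difference 1.79, the pooled SD 2.10 and d = 0.85. The t-based requirement is 22.8 per group, with 80.4% power at 23. That figure belongs to the primary comparison; no sample size or power is stated for STING.

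Expected carriers among 46 run from 46 × 0.10 = 4.6 to 46 × 0.30 = 13.8, or about 5 to 14.

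**Assumptions not in the documents.** These are the ancestry mix, and an ancestry effect δ on the response of 0.5 or 1.0 SD. Genotype is reduced to variant versus wildtype, with no true STING effect.

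**Formula.** Take share p from a population with variant frequency f, and the rest at 10%. The overall variant frequency is π = p·f + (1 − p)·0.10. The fraction of δ that appears as a genotype difference is

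L = p·f/π − p(1 − f)/(1 − π), and bias = L × δ.

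| Assumed mix | π | L | Bias at 0.5 / 1.0 SD | Unadjusted type I error at 0.5 / 1.0 SD (simulated, N = 46) |
|---|---|---|---|---|
| 80/20 Caucasian/East Asian | 0.14 | 0.06/0.14 − 0.14/0.86 = 0.266 | 0.13 / 0.27 | 6.4% / 9.5% |
| 50/50 Caucasian/East Asian | 0.20 | 0.15/0.20 − 0.35/0.80 = 0.3125 | 0.16 / 0.31 | 6.8% / 11.2% |
| 90/10 Caucasian/East Asian | 0.12 | 0.03/0.12 − 0.07/0.88 = 0.170 | 0.09 / 0.17 | 5.9% / 7.1% |
| 70/30 Caucasian/African | 0.112 | 0.042/0.112 − 0.258/0.888 = 0.084 | 0.04 / 0.08 | 4.8% to 5.7% over both |
| Single ancestry | – | 0 | 0 / 0 | nominal |

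For Caucasian/East Asian mixes L peaks at 0.325, at 60/40.

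With a correctly measured ancestry term, the 80/20 and 50/50 scenarios give type I error of 4.9% to 5.1%. When ancestry has no effect, the adjusted standard error is modestly wider. Examples are 0.456 against 0.431 SD (ratio 1.058) and 0.400 against 0.383 SD (ratio 1.044). Over the mixes tried, the cost was about 2% to 7%.

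**Does the grouping matter?** Assume a 60/20/10/10 mix in the order of the inputs.

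- Unadjusted, π = 0.06 + 0.028 + 0.018 + 0.03 = 0.136. An effect confined to East Asian participants transfers 0.03/0.136 − 0.07/0.864 = 0.14. An effect confined to African participants transfers 0.028/0.136 − 0.172/0.864 = 0.007.
- Now adjust for Caucasian versus all others. Within the pooled group the variant frequency is 0.076/0.40 = 0.19. The East Asian imbalance there is 0.03/0.076 − 0.07/0.324 = 0.179, and the African imbalance is 0.028/0.076 − 0.172/0.324 = −0.162.
- The pooled group's weight in the genotype coefficient is 0.4·0.19·0.81 / (0.4·0.19·0.81 + 0.6·0.10·0.90) = 0.0616/0.1156 = 0.53.
- Bias at 1.0 SD is then 0.179 × 0.53 = 0.095 for the East Asian-only effect, or 0.095/0.14 = 68% of the unadjusted bias. For the African-only effect it is −0.162 × 0.53 = −0.09, where there was almost none before. Simulation agrees (about 70% left; −0.08 to −0.10).
- With separate ancestry levels, the simulated bias was 0.02 SD or less, with error near 5% and a similar standard error.

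**The case against.** **The size is assumed.** Neither an ancestry effect on titres nor an ancestry mix is stated, and the recruitment text does not support a 20% to 50% East Asian share. This stands. The 6% to 11% range is conditional, and even there the bias (0.13 to 0.32 SD) is smaller than one standard error (0.43 SD).

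**The simulated contrast is not the SAP's.** The SAP has three genotype categories, and the protocol does not map its percentages to them. This also stands. The numbers show the mechanism and its order of size, and sparse genotype cells limit precision whichever model is used.

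**A race/ethnicity term may not help.** This holds for a careless grouping, as the two-level example shows. It does not hold for separate levels.

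**Age and sex.** A reader might infer that the STING analysis excludes age and sex. The documents do not establish that. Protocol section 5.C sends other endpoints to a similar ANCOVA, and the SAP sentence is under-specified. Neither text, however, supplies a race/ethnicity term.

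**Low stakes.** STING is the fourth hypothesis, a secondary analysis in a study the protocol calls a pilot. That limits the weight of the point, but the remedy is small and the data will be in hand.

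**Conclusion.** The point holds in conditional form. The plan identifies population stratification, collects race and ethnicity, and lists no such term in the STING analysis. Part of any ancestry difference in titre response can therefore appear as a STING effect.

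For an assumed effect of 0.5 to 1.0 SD, bias is about 0.13 to 0.32 SD and type I error about 6% to 11% if 20% to 50% of participants come from the 30%-frequency population. Error is about 6% to 7% at a 10% share, and there is little or no inflation in a Caucasian/African or single-ancestry sample.

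Two stronger readings are tempting and unsupported. One is that an ancestry effect passes wholly into the genotype contrast: in the two-population mixes tried, about 8% to 33% does. The other is that bias has been shown: it is possible, but nothing in the documents establishes an ancestry effect. The primary obesity comparison and its sample size are not touched.

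**What to change.** In the SAP, replace the STING sentence with a linear model of fold change on genotype, BMI group, age, sex and race/ethnicity. This also settles the unnamed second factor.

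- State how the collected race and ethnicity map to the four ancestry categories in Protocol section 3. Keep the highest-frequency group (East Asian) separate rather than pooling all non-Caucasian participants.
- Merge only empty or near-empty levels, under a rule fixed before genotypes are seen.
- Report the genotype-by-race/ethnicity table and the unadjusted contrast beside the adjusted one. Do not attribute a difference to STING if it appears only in the unadjusted contrast.

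The cost is a few lines of SAP text, 1 to 3 degrees of freedom, and a standard error about 2% to 7% wider if ancestry has no effect. With about 5 to 14 variant carriers expected among 46, precision will be limited either way.
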